6.1.3 Dose Escalation

The SRG will comprise the Investigator, Medical Monitor, Cerevance Responsible Medical Officer and may include other Cerevance representatives. A pharmacokineticist and other subject matter experts may participate as needed. The SRG will be responsible for the ongoing review of safety, tolerability, clinical laboratory results, and available PK data and deciding to:

- Escalate to the next planned cohort or alternative dose levels (e.g., lower, intermediate, or higher) in single-dose cohorts (based on a review of available data, including at least 72 hours post-dose safety data and clinical laboratory results from a minimum of 6 evaluable subjects in the current cohort),
- Escalate to the next planned cohort or alternative dose levels (e.g., lower, intermediate, or higher) in multiple-dose cohorts (based on a review of available data, including at least 48 hours post 7th dose safety data from a minimum of 6 evaluable subjects in the current cohort),
- Add additional dose cohort(s) in either the single- or multiple-dose studies,
- Increase the duration of dosing in the multiple-dose cohorts from 7 days to ≤14 days

If 2 or more subjects in a single cohort experience the same type of serious or medically adverse event, further dosing will be withheld until the SRG investigates the events. Based on this assessment, the SRG will determine if the study should be terminated or continued and whether modification of planned dose levels and/or implementation of additional safety monitoring is indicated.

For each cohort (including sentinel subjects, where applicable), the SRG will carefully review the available blinded safety, tolerability, clinical laboratory results, and available PK data to determine whether dosing should stop or continue (and, if continued, at what dose, including whether to repeat the previous dose), whether additional sequential dosing should be implemented in future cohorts or whether the blind should be broken to identify whether the subjects received CVN766 or placebo. However, precautions must be taken not to unblind the study staff, including the Investigator.

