6.3 Premature Termination or Suspension of Study or Investigational Site

6.3.1 Criteria for Premature Termination or Suspension of the Study

The study will be completed as planned unless new information or other evaluation regarding the safety of the study medication indicates an adverse change in the risk profile for the compound, such that the SRG or Institutional Review Board (IRB) considers the risk is no longer acceptable for subjects participating in the study.

In addition, if any of the following occur, further dosing will be withheld until the SRG reviews the relevant data, including unblinded data (if deemed necessary by the SRG request), and will decide whether it is safe to suspend dosing or continue dosing at either the planned or alternative dose levels or decides to prematurely terminate the study:

1. Two or more subjects in any single cohort or across more than 1 cohort experience the same type of serious or medically significant event as defined by the Investigator
2. Two or more subjects in any single cohort or across more than 1 cohort experience alanine aminotransferase (ALT) and/or aspartate aminotransferase (AST) elevations $>5 \times$ upper limits of normal (ULN) in the absence of a concomitant bilirubin increase (see point 3 below)

3. One or more subjects in any single cohort or across more than 1 cohort experience ALT and/or AST elevations $>3 \times \text{ULN}$ in the presence of a total bilirubin increase $>2 \times \text{ULN}$ or an international normalized ratio (INR) >1.5 without findings of cholestasis or other alternate etiology to explain the elevations (i.e., “Hy’s Law cases”)
4. Two or more subjects in any single cohort or across more than 1 cohort experience ALT and/or AST elevations $>3 \times \text{ULN}$ with the appearance of fatigue, nausea, vomiting, right upper quadrant pain or tenderness, fever, rash, and/or eosinophilia ($>5\%$).

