7.5 Criteria for Discontinuation or Withdrawal of a Subject

The primary reason for discontinuation or withdrawal of the subject from the study or study medication should be recorded in the eCRF using the following categories. For screen failure subjects, **Section 9.1.15**.

1. The subject has experienced a PTE or AE that requires early termination because continued participation imposes an unacceptable risk to the subject's health or the subject is unwilling to continue because of the PTE or AE.
2. Liver Function Test (LFT) Abnormalities

Study medication should be discontinued immediately with appropriate clinical follow-up (including repeat laboratory tests until a subject's laboratory profile has returned to normal/baseline status) if the following circumstances occur at any time during study medication treatment:

- ALT or AST $>8 \times$ ULN, or
 - ALT or AST $>5 \times$ ULN and persists for more than 2 weeks, or
 - ALT or AST $>3 \times$ ULN in conjunction with elevated total bilirubin $>2 \times$ ULN or INR >1.5 , or
 - ALT or AST $>3 \times$ ULN with the appearance of fatigue, nausea, vomiting, right upper quadrant pain or tenderness, fever, rash and/or eosinophilia ($>5\%$).
3. Significant protocol deviation. The discovery post-randomization that the subject failed to meet protocol entry criteria or did not adhere to protocol requirements and continued participation poses an unacceptable risk to the subject's health.
 4. Lost to follow-up. The subject did not return to the clinic, and attempts to contact the subject were unsuccessful. Attempts to reach the subject must be documented.
 5. Voluntary withdrawal. The subject (or subject's legally acceptable representative) wishes to withdraw from the study. The reason for withdrawal, if provided, should be recorded in the eCRF.

Note: All attempts should be made to determine the underlying reason for the withdrawal, and, where possible, the primary underlying reason should be recorded (i.e., withdrawal due to an AE).

6. The sponsor, IRB, IEC, or regulatory agency terminates the study.
7. Other.

Note: The specific reasons should be recorded in the “specify” field of the eCRF.

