9.8.3 Reporting of Abnormal LFT

If a subject is noted to have ALT or AST elevated $>3 \times \text{ULN}$ on 2 consecutive occasions, the abnormality should be recorded as an AE. In addition, an LFT Increases eCRF must be completed by providing additional information on relevant recent history, risk factors, clinical signs and symptoms, and results of any additional diagnostic tests performed.

If a subject is noted to have ALT or AST $>3 \times \text{ULN}$ and total bilirubin $>2 \times \text{ULN}$ for which an alternative etiology has not been identified, the event should be recorded as an SAE and reported as per **Section 9.8.2**. The Investigator must contact the Medical Monitor for discussion of the relevant subject details and possible alternative etiologies, such as acute viral hepatitis A or B or other acute liver disease or medical history/concurrent medical conditions. Follow-up laboratory tests as described in **Section 9.1.8** must also be performed. In addition, an LFT Increases eCRF must be completed and transmitted with the SAE form (as per **Section 9.8.3**).

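### In 6.3.1, two asymptomatic subjects with ALT/AST >5 x ULN force a dosing hold at normal bilirubin, but may force none if bilirubin is >2 x ULN in one or both and cholestasis or another cause is already evident

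*Protocol*

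**What the plan says.** Section 6.3.1 lists four criteria. Of these it says that "if any of the following occur, further dosing will be withheld until the SRG reviews the relevant data". The hold is mandatory once a criterion is met.

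- **Criterion 1:** two or more subjects, within or across cohorts, with "the same type of serious or medically significant event as defined by the Investigator".
- **Criterion 2:** two or more subjects with ALT and/or AST >5 x ULN, "in the absence of a concomitant bilirubin increase (see point 3 below"). It makes no exception for a known cause.
- **Criterion 3:** one or more subjects with ALT and/or AST >3 x ULN plus total bilirubin >2 x ULN or INR >1.5, "without findings of cholestasis or other alternate etiology to explain the elevations".
- **Criterion 4:** two or more subjects with ALT and/or AST >3 x ULN "with the appearance of fatigue, nausea, vomiting, right upper quadrant pain or tenderness, fever, rash, and/or eosinophilia" (>5%).

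Three other sections bear on the same cases.

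- **7.5** acts on the individual. For ALT/AST >3 x ULN with bilirubin >2 x ULN or INR >1.5 it says "Study medication should be discontinued immediately with appropriate clinical follow-up", with no exemption for a known cause.
- **9.8.3** covers ALT/AST >3 x ULN with bilirubin >2 x ULN "for which an alternative etiology has not been identified, the event should be recorded as an SAE".
- **6.1.3** says "The SRG will be responsible for the ongoing review of safety, tolerability, clinical laboratory results" and makes escalation depend on that review.

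**The concern.** Criterion 2 hands subjects with raised bilirubin to criterion 3, but criterion 3 does not accept all of them. A subject with bilirubin >2 x ULN and cholestasis or another explanation leaves criterion 2 and is refused by criterion 3. Adding raised bilirubin to the same transaminase elevations can therefore remove a mandatory hold, which is the wrong direction for a liver stopping rule.

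A found cause does not explain the difference. At normal bilirubin, criterion 2 forces a hold for two subjects even when both elevations are explained. The protocol has thus already decided that two subjects above 5 x ULN warrant SRG review whatever the cause.

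At stake is the dosing of other subjects in a first-in-human study. The multiple-dose cohorts matter most: there is no sentinel dosing, dosing runs for 7 days and may be extended to at most 14 (6.1.2), and the escalation review takes place at the end of a cohort.

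**Working it through.** The plan gives no figure to reproduce. The check applies criteria 2 and 3 as written to pairs of subjects.

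**Illustrative inputs, assumed for the check.** Both subjects have ALT 6 x ULN lasting no more than 2 weeks, no listed symptoms, no eosinophilia >5% and INR 1.0. Criterion 4 is therefore not met. Bilirubin is 0.8 x ULN (normal) or 2.5 x ULN (raised).

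**Rules.**
- Criterion 2 is met if at least 2 subjects have ALT/AST >5 x ULN without a bilirubin increase. The increase is taken as the >2 x ULN of the cross-referenced point 3.
- Criterion 3 is met if at least 1 subject has ALT/AST >3 x ULN, bilirubin >2 x ULN or INR >1.5, and no cholestasis or alternate cause.
- A 9.8.3 SAE is ALT/AST >3 x ULN with bilirubin >2 x ULN and no alternate cause. Cholestasis alone is not counted as an alternate cause here.

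| Pair | Counted by criterion 2 (needs 2) | Counted by criterion 3 (needs 1) | Hold forced by 2 or 3 | 9.8.3 SAEs |
|---|---|---|---|---|
| A. Both 0.8, any or no cause | 2 | 0 | Yes | 0 |
| B. Both 2.5, no cause found | 0 | 2 | Yes | 2 |
| C. Both 2.5, cholestasis only | 0 | 0 | No | 2 |
| D. Both 2.5, alternate cause | 0 | 0 | No | 0 |
| E. One 0.8; one 2.5, no cause found | 1 | 1 | Yes | 1 |
| F. One 0.8; one 2.5, cholestasis only | 1 | 0 | No | 1 |
| G. One 0.8; one 2.5, alternate cause | 1 | 0 | No | 0 |

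Raising INR to 1.8 does not rescue pairs C and D, because the etiology clause in criterion 3 covers the INR limb too.

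**What the other provisions do in C, D, F and G.**
- 7.5 stops each subject with bilirubin 2.5 x ULN. It does not stop the other subjects, nor, in F and G, the subject at 0.8 x ULN on these inputs.
- In C there are two SAEs of the same kind, so criterion 1 is probably met. In F there is one and in D and G none, so criterion 1 depends on the Investigator's judgement.
- SRG review can still stop dosing at its discretion.

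**Timing.** Cause is not fixed from the start. Until cholestasis or another cause has been found, a single subject at 2.5 x ULN meets criterion 3, as in B and E. The gap opens only when the finding is already there as the result is assessed. That can happen: alkaline phosphatase and GGT are in the routine chemistry panel (Table 10), so a cholestatic pattern can appear on the same report.

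**After the change.** With criterion 2 excluding only cases that already meet criterion 3, its count is 2 in A, C, D, F and G. Criterion 3 still covers B and E. Every pair forces a hold.

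**The case against.** The strongest reply is that the cross-reference exists to route bilirubin cases to the stricter one-subject rule. Criterion 2 would then exclude only what criterion 3 takes, and there would be no gap. That reading is reasonable and may be what was meant, but it is not what the words say: the exclusion turns on a bilirubin increase, not on meeting criterion 3. If it is the intent, the proposed wording simply states it. A second closing reading, that the etiology clause qualifies INR alone, is weaker because the clause speaks of explaining the elevations and ends by naming Hy's Law cases.

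It can also be said that exempting explained cases is the purpose of a Hy's Law criterion. That is fair for a rule triggered by one subject. It does not explain why two subjects who would be held at normal bilirubin, explained or not, should escape when bilirubin is higher.

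The remaining safeguards are real. ALT/AST >3 x ULN on two consecutive occasions requires contact with the Medical Monitor (9.1.12), who sits on the SRG. AEs are evaluated within and across cohorts against the termination criteria (6.1.3). The next dose level cannot start without SRG review, so the gap mainly concerns cohorts already in progress. None of these forces a hold there.

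A reader might infer more than the documents support:
- *Unexplained liver injury with jaundice escapes the rules.* It does not; criterion 3 fires on one subject.
- *The affected subjects keep receiving drug.* Those with bilirubin >2 x ULN are stopped by 7.5.
- *The gap extends to bilirubin of 1 to 2 x ULN.* That requires reading an increase as any value above ULN, whereas the pointer to point 3 more naturally supplies >2 x ULN.
- *The number of missed rows measures the risk.* The rows are chosen cases without weights and show which pairs are missed, not how often they occur.

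**Conclusion.** The point holds in a narrow form. On the plain wording, two asymptomatic subjects with ALT/AST >5 x ULN meet neither criterion 2 nor criterion 3 if one or both have bilirubin >2 x ULN with cholestasis or an alternate cause already evident at assessment. Two cholestatic cases without another cause probably reach criterion 1 through 9.8.3. What remains without a guaranteed study-level hold is two subjects with an identified alternate cause, or a mixed pair in which only one has raised bilirubin and it comes with such a finding.

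This rests on taking the exclusion in criterion 2 literally, on the etiology clause governing all of criterion 3, and on cholestasis alone not counting as an alternative etiology under 9.8.3. The documents give no basis for a frequency. Exclusion 23 removes subjects with confirmed ALT/AST >1.5 x ULN at entry, and about 64 are planned. The reason to act is that a mandatory stopping rule should not weaken as bilirubin rises, and the correction is nearly free.

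**What to change.** In criterion 2 of 6.3.1, replace "in the absence of a concomitant bilirubin increase (see point 3 below") with *not already meeting criterion 3*, or delete it. Two subjects with ALT/AST >5 x ULN would then always trigger a hold for SRG review, and criterion 3 would stay as the one-subject rule. Writing only a >2 x ULN threshold into the present qualifier would not be enough: it fixes the meaning of an increase but leaves pairs C, D, F and G uncovered.

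The change touches one qualifier and needs no added data or visits. Its downside is an occasional extra hold for SRG review when a benign cause is evident.

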6.3.2 Criteria for Premature Termination or Suspension of Investigational Sites

A study site may be terminated prematurely or suspended if the site (including the Investigator) is found in significant violation of Good Clinical Practice (GCP), protocol, or contractual agreement, is unable to ensure adequate study performance, or as otherwise permitted by the contractual agreement.

6.3.3 Procedures for Premature Termination or Suspension of the Study or the Participation of Investigational Site(s)

In the event that the sponsor, an IRB/independent ethics committee (IEC), or regulatory authority elects to terminate or suspend the study or the participation of an investigational site, a study-specific procedure for early termination or suspension will be provided by the sponsor; applicable investigational sites will follow the procedure during the course of termination or study suspension.

7.0 SUBJECT POPULATION

Screening for eligible subjects will be performed within 28 days prior to randomization or first dose.

7.1 Inclusion Criteria

Subject eligibility is determined according to the following criteria prior to entry into the study:

1. In the Investigator's opinion, the subject can understand and sign the Informed Consent Form and comply with all protocol requirements.
2. The subject is a healthy male or female adult who is 18 to 55 years of age, inclusive at the time of ICF.
3. Subject weighs at least 45 kg (99 lbs) and has a BMI between 18.0 and 32.0 kg/m^2 , inclusive at Screening.
4. A male subject who is nonsterilized* and sexually active with a female partner of childbearing potential* agree to use two forms of adequate contraception* from signing the ICF throughout the study and for 90 days after the last dose.

*Definitions and acceptable methods of contraception are defined in **Section 9.1.13 Contraception and Pregnancy Avoidance Procedure**, and reporting responsibilities are defined in **Section 9.1.14 Pregnancy**.

5. A female subject of childbearing potential who complies with contraception requirements* or a female with no childbearing potential, defined as the subject has been surgically sterilized (hysterectomy, bilateral oophorectomy) or who are postmenopausal (defined as continuous amenorrhea of at least 2 years and FSH>40 IU/L).

Note: hormonal contraceptives are not permitted for female participants, as referenced in **Table 3**. Female partners of male participants can use hormonal contraceptives.

7.2 Exclusion Criteria

Any subject who meets any of the following criteria will not qualify for entry into the study:

1. Subject has received any investigational compound within 30 days prior to the first dose of study medication or within 5 half-lives, whichever is greater.
2. Subject is a study site employee or an immediate family member of a study site employee.
3. Subject has evidence of CS neurologic, cardiovascular, pulmonary, hepatic, hematopoietic disease, renal, metabolic, gastrointestinal, urologic, immunologic, endocrine disease, serious allergy, full-body allergic skin rash (including hives), psychiatric disorder, evidence of abnormal liver function test, evidence of abnormal renal function tests or other abnormality that may impact the ability of the subject to participate or potentially confound the study results.

Note: Healthy volunteers with pre-existing stable disease, defined as diseases not requiring significant change in therapy or hospitalization for worsening disease during the 6 wks before enrolment, may be included at the discretion of the Investigator.

4. There is any finding in the subject's medical history, physical examination, or safety laboratory tests giving reasonable suspicion of a disease that would contraindicate taking CVN766 or a similar drug in the same class or that might interfere with the conduct of the study
5. Subject has a known hypersensitivity to any component of the formulation of CVN766.
6. Subject has a positive urine result for drugs of abuse at Screening or Inpatient Check-in (Day - 1).
7. Subject has a history of a major psychiatric illness or currently receiving therapy for a psychiatric condition
8. Subject has a history of drug abuse or a history of alcohol abuse (more than 14 units/week) within 1 year prior to the Screening Visit or is unwilling to agree to abstain from alcohol and drugs throughout the study.
9. Subject has taken any excluded medication, supplements, or food products listed in the Excluded Medications and Dietary Products table as listed in Table 3.

10. Male subjects who do not agree to all the following rules: when sexually active with a female partner(s) of childbearing potential during the study, and for 90 days after the last dose of study drug: a) must use two acceptable methods of birth control (condom combined with highly effective method of contraception as listed in **Section 9.1.13**). Female partners of male participants can use hormonal contraception, and this should be in place for at least 30 days prior to dosing. Male subjects must also agree to refrain from sperm donation during the study and until 90 days after the last dose of the study drug.
11. Female subjects who are pregnant or breastfeeding or plan to become pregnant or donate ova during the study or 30 days after the last dose of the study drug. Women of childbearing potential must agree to practice an acceptable method of birth control (e.g., intrauterine device, barrier, abstinence).

Note: hormonal contraceptives are not permitted for female participants, as referenced in Table 3. Female partners of male participants can use hormonal contraceptives.

*Definitions and acceptable methods of contraception are defined in Section 9.1.13. Contraception and Pregnancy Avoidance Procedure and reporting responsibilities are defined in Section 9.1.14 Pregnancy.

--

12. Subject has previously had a seizure or convulsion (lifetime, with the exception of febrile seizures), including absence seizure.
13. Subject has current or recent (within 6 months) gastrointestinal disease that would be expected to influence the absorption of drugs (i.e., a history of malabsorption, any surgical intervention known to impact absorption [e.g., bariatric surgery or bowel resection], esophageal reflux, peptic ulcer disease, erosive esophagitis, or frequent [i.e., more than once per week] occurrence of heartburn).
14. Subject has a history of cancer or other malignancy, except for basal cell carcinoma or squamous cell carcinoma that has been in remission for at least 3 years prior to Day 1.
15. Subject has a positive test result for hepatitis B surface antigen (HBsAg), hepatitis C virus (HCV) antibody, or a human immunodeficiency virus infection at Screening.
16. Subject who regularly use nicotine-containing products (including but not limited to cigarettes, electronic cigarettes, pipes, cigars, chewing tobacco, nicotine patch, or nicotine gum). The casual users (≤ 10 cigarettes/week) may participate but must agree to refrain from the time of Screening for the duration of the study or a positive urine cotinine test at Inpatient Check-in (Day -1).
17. Subject has poor peripheral venous access (defined as more than three failed attempts to cannulate).
18. Subject has donated or lost 450 mL or more of their blood volume (including plasmapheresis) or had a transfusion of any blood product within 45 days prior to Day 1.
19. Subject has an abnormal (CS) ECG at Screening or Inpatient Check-in (Day -1). Entry of any subject with an abnormal (NCS) ECG must be approved and documented by signature by the Investigator or medically qualified sub-Investigator.

20. Subject has a supine blood pressure outside the ranges of 90 to 140 mm Hg for systolic and 40 to 90 mm Hg for diastolic, confirmed with repeat per PI discretion at the Screening Visit or Inpatient Check-in (Day -1).
21. Subject has a resting heart rate outside the range of 40 to 100 bpm, confirmed with repeat per PI discretion at the Screening Visit or Inpatient Check-in (Day -1).
22. Subject has a QT interval with Fridericia’s correction method (QTcF) >450 ms (males) or >470 ms (females) or PR outside the range of 120 to 220 ms, confirmed with one repeat testing at the Screening Visit or Inpatient Check-in (Day -1) Visit.
23. Subject has abnormal Screening or Inpatient Check-in (Day -1) laboratory values that suggest a CS underlying disease or subject with the following lab abnormalities: ALT and/or AST >1.5 the ULN, confirmed with one repeat testing.
24. Subject has a risk of suicide according to the Investigator’s clinical judgment or has made a suicide attempt in the previous 2 years.

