9.1.13 Contraception and Pregnancy Avoidance Procedure

From the date of signing of ICF, throughout the duration of the study, and for 30 days after the last dose of study medication, females of childbearing potential* must use **two** acceptable methods of contraception and must agree not to donate eggs; Nonsterilized** male subjects who are sexually active with a female partner of childbearing potential* must use **two** acceptable method(s) of contraception throughout the duration of the study, and for 90 days after the last dose of study medication. In addition, males must be advised not to donate sperm for 90 days after the last dose of study medication.

Females of childbearing potential are defined as any female who has experienced menarche and who has not undergone surgical sterilization (hysterectomy or bilateral oophorectomy) and is not postmenopausal.

Menopause is defined as at least 2 years since the last regular menses with an FSH >40 IU/L or at least 5 years since the last regular menses, confirmed before any study medication is implemented. Male subjects with potentially postmenopausal partners who are under the age of 55 years must use condoms unless their partner's postmenopausal status has been confirmed by FSH level.

**Sterilized males should be at least 90 days post-vasectomy and confirm that they have obtained documentation of the absence of sperm in the ejaculate.

Acceptable and highly effective methods of contraception are:

Note: hormonal contraceptives are not permitted for female participants, as referenced in **Table 3**. Female partners of male participants can use hormonal contraceptives.

- Nonhormonal intrauterine device (IUD)
- Bilateral tubal occlusion
- Vasectomised subject/partner with documented azoospermia 90 days after the procedure, if that partner is the sole sexual partner
- Same-sex intercourse, if used consistently for the duration of the study and post-dosing as specified above

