Complete abstinence, defined as the complete avoidance of heterosexual intercourse - is an acceptable form of contraception if used consistently throughout the study and for the durations after dosing specified for males and females above. It is not necessary to use any other method of contraception when complete abstinence is elected. Females of childbearing potential who choose complete abstinence must continue to have pregnancy tests as per protocol. The reliability of sexual abstinence needs to be evaluated by the Investigator in relation to the duration of the clinical trial and the preferred and usual lifestyle of the subject.

Subjects will be provided with information on acceptable methods of contraception as part of the subject's informed consent process and will be asked to sign an ICF stating that they understand the requirements for avoidance of pregnancy, egg donation, and sperm donation during the study.

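### Exclusion 11 asks women of childbearing potential for one contraceptive method, Section 9.1.13 requires two unless abstinence is complete, and neither says whether a barrier can be the second

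*Protocol*

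**What the plan says.** Four places in the current protocol bear on contraception for female subjects.

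- **Section 7.2, exclusion 11:** "Women of childbearing potential must agree to practice an acceptable method of birth control (e.g., intrauterine device, barrier, abstinence"). The method is in the singular. The boxed note beneath adds that "Definitions and acceptable methods of contraception are defined in Section 9.1.13".
- **Section 7.1, inclusion 5:** admits "A female subject of childbearing potential who complies with contraception requirements", with an asterisk leading to the note that cites Section 9.1.13. It gives no number of methods.
- **Section 9.1.13, the rule:** from consent until 30 days after the last dose, women of childbearing potential must use two (the word is in bold) "acceptable methods of contraception and must agree not to donate eggs". For complete abstinence the second method is waived: "It is not necessary to use any other method of contraception when complete abstinence is elected".
- **Section 9.1.13, the list:** under "Acceptable and highly effective methods of contraception are" stand four entries: "Nonhormonal intrauterine device (IUD"), bilateral tubal occlusion, a vasectomised subject or partner, and same-sex intercourse. No barrier is listed. Condoms appear in this section only for male subjects whose partners may be postmenopausal. Hormonal methods are barred for female participants.

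For men, inclusion 4 and exclusion 10 both say two methods, and exclusion 10 spells them out as a condom together with a highly effective method from Section 9.1.13.

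**The concern.** The eligibility sentence is weaker than the rule it is meant to apply. Staff who check eligibility against Sections 7.1 and 7.2 meet the two-method requirement for men twice and for women not at all. A site that took exclusion 11 at its word could accept a woman on a single method. The case that matters is a barrier alone, because an IUD is at least on the list of highly effective methods.

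At stake is pregnancy exposure to a compound not previously given to humans. The current protocol has two sites, so two teams must read the same wording alike. A practical question follows as well: with hormonal methods barred, a barrier is the obvious second method for many women, and the protocol does not tell sites whether it counts.

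**Working it through.** No figure is involved, so the check is a comparison of texts.

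**Step 1. Which rule governs?** Inclusion 5 and the boxed note lead to Section 9.1.13. Section 9.1.16 requires every inclusion criterion to be met and no exclusion criterion to apply. Section 13.2 permits no exemptions. A woman on one method, short of complete abstinence, therefore fails inclusion 5 whatever exclusion 11 says. The stricter rule governs.

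**Step 2. Test each example against both texts.**

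| Practice | Exclusion 11 as worded | Section 9.1.13 |
|---|---|---|
| IUD alone | met | not met: listed, but one method of two |
| Barrier alone | met | not met: one method of two, and not listed |
| Complete abstinence | met | met, second method waived |
| Two listed methods | met | met |
| Listed method plus barrier | met | unclear |

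Of the 3 examples, 2 fall short of the governing rule when used alone and 1 satisfies it, if abstinence is complete. Whoever meets Section 9.1.13 also meets exclusion 11, but the reverse does not hold.

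**Step 3. Does a barrier count as the second method?** The text points both ways.

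- *Against:* Section 9.1.13 is named as the place where acceptable methods are defined, and its list has no barrier.
- *For:* the list heading couples acceptable with highly effective, so the entries can be read as the highly effective tier only.
- *For:* exclusion 10 counts a condom as one of a man's two acceptable methods, although it is not on the list. The protocol thus already accepts an unlisted method as one of the two.
- *For:* the list also omits hormonal methods, which the note above it allows for female partners of male participants. It is not a complete inventory of what the protocol permits.
- *For:* if the list were exhaustive, a heterosexually active woman could choose only from IUD, tubal occlusion and a vasectomised sole partner. Two are needed from three, which gives 3 possible pairs. A woman with an IUD whose partner is not vasectomised would also need tubal occlusion. That is a very narrow reading of a two-method rule.

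The last row of the table therefore stays open. The one-against-two conflict in the first two rows does not depend on how it is settled.

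**The case against.** The strongest reply is that the protocol already resolves the conflict. Inclusion 5 and the boxed note send the reader to Section 9.1.13, and all criteria apply together without exemption. Section 9.1.13 adds a further check at consent: "Subjects will be provided with information on acceptable methods of contraception as part of the" consent process. For harm to follow, a site would have to read one sentence, skip the box beneath it and overlook inclusion 5. A serum pregnancy test at Screening, a urine test on Day -1 and inpatient dosing limit the consequence further.

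Most of this stands. It makes wrongful enrolment unlikely and keeps the point small. It does not correct the sentence, which still understates a pregnancy-safety rule in the place where eligibility is decided. The safeguards are also partial: no pregnancy test is scheduled after the final dosing period. Confinement may end 72 hours after a single dose or 48 hours after the last multiple dose, while the contraception rule runs for 30 days after the last dose.

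A reader might go further and infer that Section 9.1.13 forbids barriers for women, so that exclusion 11 names a prohibited method. The documents do not support that. It needs the list to be exhaustive, and exclusion 10 shows that it is not for men.

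**Conclusion.** The point holds as an inconsistency of wording. Exclusion 11 asks for one method where the governing rule asks for two, and two of its three examples, used alone, do not satisfy that rule. This rests only on the singular in exclusion 11, the two-method requirement and the abstinence waiver in Section 9.1.13, all of which are explicit.

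The status of a barrier as second method is unclear, and the finding goes no further than that. It would also be wrong to infer that women will in fact be enrolled on one method. The number affected is not stated and cannot be derived, and the consent form is not available to check.

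Severity is low. No endpoint, analysis set, escalation rule or other statistical result is affected.

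**What to change.** - **Exclusion 11:** reword it so that women of childbearing potential agree either to two acceptable methods as set out in Section 9.1.13 or to complete abstinence. Remove the implication that an IUD or a barrier suffices alone.
- **Section 9.1.13:** state whether a barrier counts as a woman's second method beside a listed highly effective one, as exclusion 10 does for men. This is a clinical decision for the sponsor. Do not simply delete the barrier example: if a barrier is the intended second method, deletion would remove the only place where the protocol names it for female subjects.
- **Consent form:** check that it matches.

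The cost is one sentence in each of the two sections and the consent check. Design, visits and analysis are unchanged.
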